3. INR > 1.5
4. Patients with uncorrectable coagulopathy.
5. Currently breastfeeding or pregnant (latter confirmed by serum pregnancy test).
6. Physical or psychological condition which would impair study participation.
7. ASA (American Society of Anesthesiologists) score of > 4.
8. Any other loco-regional therapies at the target lesion(s) within 30 days of the ablation procedure.

NUMBER OF PARTICIPANTS

Preliminary retrospective data on the control arm suggest that a minimum ablation margin (MAM) of 2mm (SD 2) is generally achieved when ablation is performed without the use of software guidance. A sample size of 50 evaluable subjects in each group will have 80% power to detect a difference in means of -1.132 (the difference between a control arm mean, of 2 mm and the experimental arm mean of 3.132) assuming that the common

standard deviation is 2 using a two group t-test with a two-sided 0.05 significance level.

Assuming an accrual rate of 35 patients per year, the study accrual duration will be around 3 years, with follow-up for at least 2 years, totaling 5 years for the entire study duration. We will have an interim look for superiority once half the evaluable subjects (n=50) have been enrolled. A Lan-Demets spending function using an Obrien-Flemming boundary will be used for superiority stopping boundaries. We will stop enrollment at the control arm at our interim look if our p-value is less than 0.003. East v6.5 was used for sample size calculation. The next 50 patients would be enrolled on the experimental arm only to allow further development of the proposed biomechanical model on clinical practice, as well allow other interventional radiologists at our Department to utilize it.

We plan to screen 140 subjects and expect approximately 20 subjects to be screen failures. Furthermore, subjects after randomization who drop out due to tumor progression, inability to clearly depict target lesions, and major complications precluding further ablation will be considered inevaluable. To account for an expected 20% inevaluable subjects, we will enroll a total of 120 subjects to ensure 100 evaluable subjects.

STUDY PLAN/DESIGN

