Figure 4: Image fusion of pre- and post-ablation contrast-enhanced CT using the proposed biomechanical model-based deformable image registration (Morfeus). Blue line: deep learning-based segmentation of the liver; Red line: gross-tumor volume (GTV) contouring; Green line: gross-ablation volume. A minimal ablation margin of < 5 mm was detected on the latero-posterior aspect of the GTV (arrow).

need for re-ablation between the two cohorts will be analyzed to identify the impact of this model on intra-procedural decision-making.

C. Impact on local tumor control

Rates of local recurrence following ablation in the most recent series varies from 20% to 45%. Although re-ablation on a different session is a feasible option in a minority of patients with recurrence at the ablated tumors, this incurs several disadvantages associated with the need to undergo another invasive procedure such as emotional stress, increased exposure to complications related to anesthesia and ablation procedure, radiation exposure, additional use of intravenous contrast media, and

increased associated costs. Given the complex volumetric and spatial changes of the liver post-ablation, the ability to map the previous treatment onto the new treatment plan is critical not only to avoid treatment related toxicities, but also to ensure that the patients receive adequate treatment with optimal coverage. We hypothesize that the use of this current model might improve local tumor control rates at 2-years follow-up. The completion of this aim will evaluate our hypothesis that the applied biomechanical model will improve local tumor control at 2-year when compared to the standard of care control arm.

Note: Final Analysis (n = 100 evaluable subjects)

Figure 5: Clinical Trial schema

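### Enrolling 120 with 20% expected to be inevaluable yields 96 evaluable patients, not 100; the two totals agree only at about 16.7%

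*Combined protocol and SAP*

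**What the plan says.** All but one of the relevant statements are in the Number of Participants section.

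- Power: "A sample size of 50 evaluable subjects in each group will have 80% power to detect a difference in means of -1.132", with the further conditions that the common "standard deviation is 2 using a two group t-test with a two-sided 0.05 significance level".
- Screening: "We plan to screen 140 subjects and expect approximately 20 subjects to be screen failures".
- Inflation for losses: "To account for an expected 20% inevaluable subjects, we will enroll a total of 120 subjects to ensure 100 evaluable subjects". The sentence before it defines inevaluable patients as those lost after randomization, through tumor progression, target lesions that cannot be clearly seen, or major complications.
- Interim analysis: "We will have an interim look for superiority once half the evaluable subjects (n=50) have been enrolled", with the rule "We will stop enrollment at the control arm at our interim look if our p-value is less than 0.003" and, if that rule is met, "The next 50 patients would be enrolled on the experimental arm only".

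The note to Figure 5 in section 1.8 repeats the total: "Note: Final Analysis (n = 100 evaluable subjects)".

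The documents give no other loss rate and no rule for replacing inevaluable patients.

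**The concern.** A loss rate, an enrolment total and an evaluable total are tied together by one equation, and the three values given do not satisfy it. The stated 120 is what results from adding 20% to the evaluable target, rather than dividing the target by the proportion expected to remain.

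At stake is whether the trial can expect the 100 evaluable patients on which its power statement is conditioned. The same 100 underlies the interim look at half, the 0.003 threshold and the final-analysis number, and apparently the 50 patients who would follow an early stop. A correction made in only one of these places could therefore create a new mismatch.

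**Working it through.** **Inputs** (Number of Participants, unless noted): 50 evaluable per arm; difference 1.132 mm; SD 2 mm; two-sided 0.05 two-sample t-test; 140 screened, about 20 screen failures; 20% inevaluable; 120 enrolled; 100 evaluable. Allocation is 1:1 (section 1.8 and Statistical Methods).

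**1. Reproduce the plan's power.** The noncentrality is δ/(σ√(2/n)) on 2n − 2 degrees of freedom. For n = 50 this is 1.132/(2 × √(2/50)) = 1.132/0.400 = 2.83. Power from the noncentral t distribution is 80.0%. The power statement is correct for 50 evaluable per arm.

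**2. Decide what the 20% applies to.** Screening gives 140 − 20 = 120. Inevaluability arises after randomization, so its base is the 120 enrolled.

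**3. Check the inflation.**

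| Held fixed | Calculation | Result |
|---|---|---|
| 120 enrolled, 20% loss | 120 × (1 − 0.20) | 96 evaluable, 48 per arm |
| 120 enrolled, 100 evaluable | 1 − 100/120 | 16.7% loss |
| 100 evaluable, 20% loss | 100/(1 − 0.20) | 125 enrolled (126 for equal arms) |
| 20% taken of the 100 | 100 × 1.20 | 120 enrolled, the plan's figure |

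Only the last row returns 120, and there 20% is not a rate among those enrolled.

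**4. Power at 48 per arm.** Noncentrality: 1.132/(2 × √(2/48)) = 1.132/0.408 = 2.77. Power is 78.4%, a loss of about 1.7 points (80.02 − 78.36 = 1.66). The difference detectable with 80% power rises from 1.132 to 1.156 mm.

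**5. Power with the planned interim look** (normal approximation): 80.6% at 50 per arm with the look at 50% information. It is 79.0% at 48 per arm, whether the look is at 50% or 52%. The loss is 1.6 points.

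**6. Interim threshold.** O'Brien-Fleming-type Lan-DeMets spending at one-sided 0.025 spends 2[1 − Φ(2.241/√t)] by information fraction t; the two-sided interim p-value is twice that.

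- t = 0.500 (50/100 or 48/96): 0.00305, which reproduces the plan's 0.003.
- t = 50/96 = 0.521: 0.0038.

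**7. Chance of reaching 100.** If each of 120 patients independently has a 20% chance of being inevaluable (an assumption), the probability of at least 100 evaluable is about 21%.

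**The case against.** The strongest reply is that 100 evaluable is the design target and enrolment is derived from it, so only the last step, from 100 to 120, is faulty. The power statement is expressly conditional on 50 evaluable per arm, and the interim look is counted in evaluable patients. Correcting the rate, or enrolling 125, would leave all of these untouched. That is right: the knock-on changes arise only if the plan keeps both 120 and 20%.

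The conventional correction, 125 enrolled, also preserves the target and the power, whereas accepting 96 lowers both to protect the one miscalculated number. That is a fair argument about which remedy to choose. It does not remove the inconsistency.

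Three further points have some weight.

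- The plan speaks of the next 50 patients without calling them evaluable, so they may not be the remainder of the total.
- A Lan-DeMets boundary is designed to adapt to the information fraction. Keeping 0.003 at 52% information would be slightly conservative and would not threaten the type I error.
- The 20% is itself a planning guess. With independent losses the SD of the evaluable count is √(120 × 0.2 × 0.8) ≈ 4.4, so a gap of 4 is less than one SD.

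These points keep the matter minor. None of them makes 20%, 120 and 100 agree: screen failures are counted separately, and there is no replacement rule to close the gap.

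**Conclusion.** The error is real and minor. At a 20% post-randomization loss, 120 enrolled gives an expected 96 evaluable, 4 fewer than stated (2 per arm). Power falls by about 1.6 to 1.7 points, to 78.4% in the fixed design or 79.0% with the interim look. If the intended expectation was 20 losses among 120, the rate is mislabelled, nothing is lost, and power is as stated. The documents do not show which was meant.

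The figure of 48 per arm assumes 1:1 allocation throughout and equal loss in both arms. It would not apply if control enrolment stopped at the interim look.

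**What to change.** The sponsor should say which figure was intended and make the text agree in one of these ways.

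**(a) If 20 losses among 120 was meant:** restate the expected inevaluable rate as about 16.7%. This changes one figure in one sentence and leaves the design, patient numbers and power as they are.

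**(b) If 20% is the real expectation and 120 is kept:** state 96 expected evaluable and change the figures that depend on it.

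- Power statement: 48 per group, about 78% power for 1.132 mm.
- Interim look: move it to 48, half of 96, where 0.003 remains valid; or keep it at 50 and recompute the threshold at 52% information, about 0.0038.
- The 50 patients after an early stop: 96 − 48 = 48 or 96 − 50 = 46 respectively, but only if that number was meant as the remainder of the total.
- Figure 5 note: final analysis on 96 instead of 100.

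This adds no patients. It changes up to five linked figures and lowers the stated power by about 1.6 to 1.7 points.

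Enrolling 125 (126 for equal arms) would also reconcile the numbers and keep 100 evaluable with 80% power, at the cost of 5 or 6 more patients. For a discrepancy of this size, (a) or (b) is the cheaper correction.

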1.8 Method

RayStation® is a flexible, innovative treatment planning system. It combines unique features like unmatched adaptive therapy capabilities, multi-criteria optimization,

optimization for HDR brachytherapy and external beam therapy with photons, electrons, protons as well as helium and carbon ions. RayStation supports a wide range of treatment machines, providing one control center to create biomechanical deformable registrations using “Morpheus”. Morpheus lets the investigators focus all their skill and experience on evaluating and refining plan quality.

To investigate the impact of the proposed biomechanical model on clinical decisions during ablation guidance and end-point assessment, patients will be randomized in two treatment arms (i.e. experimental arm - including anatomical modeling of the liver, and control arm) with a 1:1 ratio. The primary objective is to assess whether applying biomechanical models during percutaneous ablation will increase the minimal ablation margins, which will be evaluated at the end of the procedure with the proposed software on both cohorts. Additionally, two other distinct end-points will be analyzed: ability of the model to provide tumor identification for ablation probe placement on intra-procedural non-contrast enhanced CT, and local tumor control rates achieved with the clinical application of this model. Operating physicians will be informed in respect which arm the patient was randomized at the time of ablation (figure 3).

[figure not shown]

Figure 3: Patient randomization flowchart

A. Impact on tumor targeting

The clinical trial will be designed according to the optimized parameters from our retrospective analysis. The optimized biomechanical models will be used to assess the accuracy (e.g. the ability of the model to accurately describe the motion, deformation, and volume change and tumor location in the liver between the pre-ablation contrast-enhanced CT and the intra-procedural non-contrast enhanced CT) in both cohort of patients. For the control arm, no information in respect tumor location and targeting will be provided for the operating physician during ablation. Imaging processing using the biomechanical model will be performed after procedure completion. For the experimental

arm, tumor location and confirmation of appropriate targeting with ablation probe will be performed intra-procedurally utilizing the proposed software. Differences in tumor targeting accuracy between the two cohorts will be evaluated. If the accuracy of the cross validation cohort is not statistically significantly different, using a paired Student's T-test based on the preliminary retrospective results with significance defined as a p value of less than 0.05, from the initial optimization and validation results, then the model will be identified as complete. If the results are statistically worse, as an alternative approach, the initial cohort of patients will be used to perform an independent optimization of the model. Collaborations with the statistician will ensure that the appropriate power study has been performed for the analysis. The completion of this investigation will provide the accuracy of the present model in identifying and facilitate targeting of the liver tumors eligible for ablation when compared to the currently utilized standard of care tumor for tumor identification and targeting.

B. Impact on minimal ablation margins

A post ablation contrast-enhanced CT will be performed as per standard of care to assess the minimal ablation margins. Such assessment is currently performed manually using local rigid anatomic landmarks of the liver between the pre-ablation and post-ablation contrast-enhanced CTs. In this aim, we will evaluate the impact on the use of the advanced biomechanical model-based deformable alignment incorporating motion, deformation, and ablation-related volume loss in the liver between the pre-ablation contrast-enhanced CT and the post-ablation contrast-enhanced CT. The model will

automatically generate a minimal ablation margin on a three-dimensional Cartesian plan.

Such information will be utilized by the operator physician on the experimental arm to determine whether additional ablation is needed at a particular region surrounding the target tumor using a cut-off of at \geq 5 mm of minimal ablation margins in relation to the tumor borders in all planes (treatment arm). The \geq 5 mm minimal ablation margin will be used to account for the margin of error of the software, which is currently 3 mm. Frequency of total coverage of the target tumor, minimal ablation margins distance, and

[figure not shown]
Figure 4: Image fusion of pre- and post-ablation contrast-enhanced CT using the proposed biomechanical model-based deformable image registration (Morfeus). Blue line: deep learning-based segmentation of the liver; Red line: gross-tumor volume (GTV) contouring; Green line: gross-ablation volume. A minimal ablation margin of < 5 mm was detected on the latero-posterior aspect of the GTV (arrow).

need for re-ablation between the two cohorts will be analyzed to identify the impact of this model on intra-procedural decision-making.

C. Impact on local tumor control

Rates of local recurrence following ablation in the most recent series varies from 20% to 45%. Although re-ablation on a different session is a feasible option in a minority of patients with recurrence at the ablated tumors, this incurs several disadvantages associated with the need to undergo another invasive procedure such as emotional stress, increased exposure to complications related to anesthesia and ablation procedure, radiation exposure, additional use of intravenous contrast media, and

increased associated costs. Given the complex volumetric and spatial changes of the liver post-ablation, the ability to map the previous treatment onto the new treatment plan is critical not only to avoid treatment related toxicities, but also to ensure that the patients receive adequate treatment with optimal coverage. We hypothesize that the use of this current model might improve local tumor control rates at 2-years follow-up. The completion of this aim will evaluate our hypothesis that the applied biomechanical model will improve local tumor control at 2-year when compared to the standard of care control arm.

Note: Final Analysis (n = 100 evaluable subjects)

Figure 5: Clinical Trial schema

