for implicitly deformed structures (i.e. the kidneys) on average. Target registration error (TRE) ranged from 2.0 mm on prostate MR to 5.1 mm on lung MR on average, within 0.1 mm or lower than the image voxel sizes. Accuracy was not overly sensitive to changes in the material properties or variability in structure segmentations, as changing these inputs affected DTA and TRE by ≤ 0.8 mm. Maximum DTA > 5 mm occurred for 88% of the structures evaluated although these were within the inherent segmentation uncertainty for 82% of structures. Differences in accuracy between the commercial and in-house research implementations were ≤ 0.5 mm for mean DTA and ≤ 0.7 mm for mean TRE.

Deformable image registration for multi-modality imaging for treatment planning and guidance has been an area recent advancement. The vast majority of algorithms rely on voxel-based similarity metrics (e.g. mutual information) combined with geometric-based smoothing parameters (e.g. B-splines) (30, 31). The accuracy of these algorithms is often sufficient when contrast is present in the images and the motion is smooth, however, recent studies, such as the one illustrated in Figure 2(32), have indicated that as contrast is reduced and the motion is complex and non-uniform, the accuracy reduces substantially (33-35). In several instances (e.g. contrast-limited images, sliding interfaces) biomechanical models have succeeded in achieving the desired level of accuracy (8, 9, 11, 17, 18, 20, 21). The successful completion of this program of research will expand these proven models to model deformation observed between planning and intra-procedural images for percutaneous ablation (PTA). The development of these models, which maintain accuracy regardless of extent of contrast in the images, will enable the safe use of deformable registration for PTA guidance (integration of pre-treatment

images) and PTA response (e.g. water loss and tissue retraction due to heating and inflammation).

[figure not shown]

Figure 2. Two methods of dose accumulation were evaluated by deforming a gel dosimeter. Morpheus was more accurate at representing the actual deformation.

ELIGIBILITY

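### The biomechanical model is declared complete when a t-test is non-significant, which does not show that its registration accuracy is maintained; no tolerable loss, cohort definition or pairing is given

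*Combined protocol and SAP*

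**What the plan says.** Section 1.8 Method, A (Impact on tumor targeting) assesses how well the model describes motion, deformation, "volume change and tumor location in the liver between the pre-ablation contrast-enhanced CT and the intra-procedural non-contrast enhanced CT". This serves one of two further end-points named earlier in section 1.8: "ability of the model to provide tumor identification for ablation probe placement on intra-procedural non-contrast enhanced CT".

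The rule for accepting the model has two branches:

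- **Accept.** "If the accuracy of the cross validation cohort is not statistically significantly different, using a paired" Student's t-test against the preliminary retrospective results at p < 0.05, "from the initial optimization and validation results, then the model will be identified as complete".
- **Re-optimize.** "If the results are statistically worse, as an alternative approach, the initial cohort of patients will be used" for an independent optimization.

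On sample size it says only: "Collaborations with the statistician will ensure that the appropriate power study has been performed for the analysis". No number of patients, SD or difference to detect is given. The Analysis Plan under Statistical Considerations does not mention this test.

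**The concern.** The rule reads a failure to reject as proof of sameness. A non-significant result can mean that accuracy is unchanged, or that the data are too few or too variable to show a real loss. The incentive therefore runs the wrong way: the weaker the data, the more likely the model is to be accepted.

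The test also cannot be set up from the text. The term for the cross-validation cohort occurs only here, while in the surrounding sentences the two cohorts are the randomized arms. A paired test needs two measurements on the same unit, yet one cohort is compared with earlier retrospective results and no pair is named. Accuracy is described by example, without a metric or unit.

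At stake is whether the model is accepted or re-optimized for locating the tumor on the intra-procedural non-contrast CT. As written, that verdict depends on sample size and noise as well as on accuracy.

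**Working it through.** **The plan's own figure.** The only sample-size calculation (Number of Participants) is for the minimal ablation margin: 50 per group, difference 1.132 mm, SD 2 mm, two-sided 0.05. The noncentrality is 1.132 / (2 × √(2/50)) = 2.83 on 98 degrees of freedom, which gives 80.0% power. It reproduces, but it is a superiority calculation for a different quantity and does not cover the accuracy test.

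**Inputs for the accuracy test.** The documents give alpha = 0.05 and nothing else. Assumed here: two-sided testing; SD 1.5, 2 or 3 mm (for pairs, the SD of the differences); true loss 0.5, 1.0 or 2.0 mm; n = 20 or 50.

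**Formula.** The probability of being called complete is P(|T| < t at 0.975), with T noncentral t.

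- Independent cohorts, n each: noncentrality = loss / (SD × √(2/n)), df = 2n − 2.
- Pairs: noncentrality = loss / (SD / √n), df = n − 1.

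Example: loss 1.0 mm, SD 2 mm, 50 v 50. Noncentrality = 1.0 / (2 × 0.2) = 2.5, critical value 1.984, acceptance 0.303.

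**Chance that a worse model is called complete**

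| True loss | Design | SD 1.5 mm | SD 2 mm | SD 3 mm |
|---|---|---|---|---|
| 0.5 mm | 50 v 50 | 62% | 76% | 87% |
| 0.5 mm | 50 pairs | 36% | 59% | 79% |
| 1.0 mm | 50 v 50 | 9% | 30% | 62% |
| 1.0 mm | 50 pairs | 0.4% | 7% | 36% |
| 1.0 mm | 20 v 20 | 46% | 66% | 82% |
| 1.0 mm | 20 pairs | 19% | 44% | 71% |
| 2.0 mm | 50 v 50 | <0.1% | 0.1% | 9% |

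A simulation of 40,000 runs at loss 1.0 mm and n = 50 agrees: Welch 0.091/0.302/0.623, paired 0.004/0.064/0.365.

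The same 1.0 mm loss therefore passes between 0.4% and 82% of the time, depending on n, noise and pairing, none of which the plan fixes. A 2.0 mm loss is caught at least 91% of the time at n = 50.

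**Does another figure supply a tolerable loss?** Two come close.

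- Section 1.8 B sets its 5 mm cut-off to allow for the "margin of error of the software, which is currently 3 mm". That is the present error of the tool, not a loss the investigators would accept, and it is not tied to this rule.
- Section 1.5 reports: "Differences in accuracy between the commercial and in-house research implementations were" at most 0.5 mm for mean distance to agreement and 0.7 mm for mean target registration error, and regards the two as equally accurate. This suggests that the 0.5 mm rows may not matter in practice, but the plan does not say what loss would.

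**The case against.** The strongest reply is that little hangs on the rule. It is absent from the listed objectives and from the statistical section, and it leads only to a label or a later optimization. No randomization, stopping or trial conclusion depends on it. That stands, and it keeps the point minor. The same software also measures the primary endpoint, but that is no reason to raise the weight: the rule concerns registration to the non-contrast intra-procedural CT, while margins are measured between the pre- and post-ablation contrast CTs.

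Second, the comparator is partly described, as the preliminary retrospective results, and accuracy is to be assessed in both arms. The flowchart and schema figures are also not available to this review. This is fair, but the text still does not say which patients form the cross-validation cohort, which form the initial cohort, or what is paired with what.

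Third, power is deferred, not ignored, and a power study must name a difference to detect. It could reduce the small-sample problem. It would not make non-significance evidence of maintained accuracy, and no tolerable loss is stated for it to use.

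Fourth, the magnitudes rest wholly on assumed inputs. This is correct: they show how the rule behaves and are not an estimated error rate for this trial.

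Fifth, at the illustrated margins the replacement rule re-optimizes a model with a 1.0 mm loss about as often as the present one (0.91/0.70/0.38 under both). This is true. The gain is that fewer such models are called complete.

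**Conclusion.** The concern holds, as a minor point. Followed as written, the rule can certify a model whose registration accuracy has fallen, and does so more readily with fewer or noisier data. Under the assumed SDs of 1.5 to 3 mm, a true 1.0 mm loss is accepted 9 to 62% of the time with 50 v 50 patients, 0.4 to 36% with 50 pairs, and up to 82% with 20 v 20. Large losses are mostly detected at n = 50. The logical fault does not depend on these assumptions; its size does. Whether a paired test is suitable cannot be judged until the cohorts and the pairs are defined. The primary sample size and analysis are unaffected.

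**What to change.** In section 1.8 A, define the two cohorts, the accuracy measure (for example registration error in mm) and the unit of analysis. Then replace the rule with text such as:

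> The difference in mean registration error (trial minus retrospective cohort) will be estimated with a 95% confidence interval (Welch if the cohorts are different patients, paired if the same patients or landmarks are measured twice). The model will be identified as complete only if the upper limit for the loss of accuracy is below a margin fixed and justified before the trial data are examined. If this criterion is not met and the lower limit is above zero, the planned independent optimization will be done. If it is not met and the interval includes zero, the estimate and interval will be reported without a completion verdict.

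Base the promised power study on that margin.

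**Cost.** A text change and one sponsor decision, the margin. An unchanged model may miss the criterion if the margin is tight or the cohorts are small. For an 80% chance of passing, the margin must be about 0.85/1.13/1.70 mm (50 v 50) or 0.61/0.81/1.21 mm (50 pairs) at SD 1.5/2/3 mm. At the 50 v 50 margins:

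| True loss | Complete | Re-optimized | No verdict |
|---|---|---|---|
| None | 80% at each SD | 2 to 3% | about 18% |
| 1.0 mm | 0.7/5/21% | 91/70/38% | 8/25/41% |

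At SD 2 and 3 mm the 1.0 mm loss lies inside the margin, so calling it complete is then not an error.

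One branch changes: a statistically worse result whose upper limit is still below the margin would count as complete. With 50 v 50 this needs a margin wider than the whole interval, 2 × 1.984 × SD × √(2/50) = 1.19/1.59/2.38 mm. These figures show feasibility and are not proposed margins.

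### The software that guides the ablation also measures the primary margin; the plan lets the model change, and no rule keeps the measuring version constant.

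*Combined protocol and SAP*

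**What the plan says.** All places are in the combined protocol and SAP.

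- **The instrument.** Section 1.8 Method says of the primary margins: "which will be evaluated at the end of the procedure with the proposed software on both cohorts". Part B adds that the model will "automatically generate a minimal ablation margin on a three-dimensional Cartesian plan". In the experimental arm the operator uses the same output to decide on further ablation.
- **The starting point.** Section 1.8, part A: "The clinical trial will be designed according to the optimized parameters from our retrospective analysis".
- **First route to a change.** Also in part A, accuracy in a cross-validation cohort is compared with the retrospective results. If it does not differ significantly, "then the model will be identified as complete". Should accuracy turn out significantly lower, the fallback named there is that "the initial cohort of patients will be used to perform an independent optimization of the model". Neither cohort is defined, and no date or patient count is given for the test.
- **Second route.** Under Number of Participants, if the interim p-value is below 0.003, control enrolment stops and the next 50 patients all enter the experimental arm, "to allow further development of the proposed biomechanical model on clinical practice".
- **The analysis.** Statistical Considerations, Analysis Plan, compares average margins between the arms at the end of the study by a two-sample t-test or Wilcoxon test. It has no term for software version or calendar period, and it does not say whether patients enrolled after a control-arm stop are included.

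The documents contain no version lock, no recording of the version used per patient, and no rule for re-reading earlier scans.

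**The concern.** A primary endpoint that is a software output is comparable across patients only if the same software settings produce it. If the model is re-tuned between patients, margins read before and after the change may sit on different scales, and patients used for tuning may also be measured by the tuned model.

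The effect depends on how version is distributed over the arms. With concurrent 1:1 allocation, and both arms read on the same versions, a shift in the reading falls on both arms alike and acts as noise. Once only experimental patients are enrolled, a new version would apply to that arm alone. If those patients were pooled with the randomised ones, a change in the instrument would be counted as a treatment effect in the final estimate and its confidence interval.

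**Working it through.** **Inputs.** From Number of Participants: 50 evaluable per arm, difference 1.132 mm, SD 2 mm, two-sided alpha 0.05, power 80%, interim look at 50 evaluable patients (25 per arm) with threshold p < 0.003, then 50 experimental-only patients after a stop. From 1.5 Mechanism: the passage beginning "Differences in accuracy between the commercial and in-house research implementations were" gives at most 0.5 mm (mean distance to agreement) and 0.7 mm (mean target registration error). From 1.8 Method, part B: a software margin of error of 3 mm.

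**Assumption.** The documents give no figure for how far a re-tuned version would move the margin reading. I write this shift as s and use 0.5 to 0.7 mm as a working range, with 1 and 3 mm to show sensitivity. None of these is a documented version effect.

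**1. The plan's own figures.** Non-centrality = 1.132 / (2 × √(2/50)) = 2.83. The two-sided t-test on 98 degrees of freedom has power 80.0%, as stated. A Lan-DeMets O'Brien-Fleming boundary at half the information gives an interim two-sided p of 0.0031, consistent with the stated 0.003. Neither figure is in dispute.

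**2. Version changes under 1:1 allocation, half of each arm on each version.** The arm difference is unbiased. The variance rises by s²/4, so SD = √(4 + s²/4).

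| s (mm) | SD (mm) | Power |
|---|---|---|
| 0 | 2.00 | 80.0% |
| 0.5 | 2.02 | 79.4% |
| 0.7 | 2.03 | 78.8% |
| 1 | 2.06 | 77.6% |
| 3 | 2.50 | 61.1% |

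**3. Chance of reaching the early-stop branch.** With 25 per arm, non-centrality = 1.132 / (2 × √(2/25)) = 2.00. The chance of p < 0.003 by t-test on 48 degrees of freedom is 14.5%, about 15%. With no true effect it is 0.3%.

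**4. Bias if that branch is reached, all 50 later patients are read on a changed version, and they are pooled.** The experimental arm has 25 + 50 = 75 patients, of whom 50/75 = 0.667 are on the new version. The control arm has 25, all on the old one. Bias = 0.667 × s.

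- s = 0.5 mm: 0.33 mm, or 0.333/1.132 = 29% of the planned difference.
- s = 0.7 mm: 0.47 mm, or 0.467/1.132 = 41%.

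**5. With one locked measuring version.** s = 0 and SD = 2 mm, so power returns to 80.0% with no change in sample size.

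**The case against.** The other side has a substantial case.

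- **Timing.** A reader might infer that the plan schedules re-optimisation in mid-trial. It does not. No timing is stated, the initial cohort could be the retrospective one, and an end-of-study validation with later re-tuning is an equally natural reading. On that reading this clause changes no trial margin. This stands.
- **Location.** The clause is in the tumor-targeting part, which registers pre-ablation CT to non-contrast intra-procedural CT. The margin uses pre- and post-ablation contrast CT. That re-tuning for one alters the other is not stated, although section 1.8 presents both as uses of the proposed model.
- **Further development.** In the sample-size section this may mean wider clinical experience, since the same sentence mentions use by other radiologists. It does not say that the software will be altered, but neither does it rule that out.
- **Size.** The 0.5 and 0.7 mm are accuracy differences between two implementations. They are not signed shifts in a margin and not effects of re-tuning. This stands, and the resulting bias cannot be read as expected.
- **False positives.** A reader might infer an inflated type I error. After an early stop, superiority has already been declared on randomised patients, so later pooling could distort the estimate but could not create that finding.
- **Pooling.** No text says the later patients join the comparison. No text excludes them either, and the arms are compared at the end of the study. Restricting the analysis to concurrent patients would remove the step 4 bias even without a version lock.

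None of this supplies the missing rule. The same software guides and measures, and nothing holds the measuring version constant.

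**Conclusion.** The point holds as a conditional risk. The plan permits the model to change and has no safeguard for the endpoint; it does not show that a change will occur.

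On the main path, with 1:1 allocation and both arms read on the same versions, the harm is a small power loss: about 79% against 80% for an assumed shift of 0.5 to 0.7 mm. It would be larger only if the shift were well above 1 mm, and the documents give no reason to expect that.

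On the early-stop path, which has about a 15% chance under the planning assumptions, the final estimate would be biased by two thirds of the shift. That requires the software to have changed, all 50 later patients to be read on the new version, and those patients to be pooled. The figure of 0.33 to 0.47 mm (29 to 41% of 1.132 mm) illustrates this chain. It is neither an expected bias nor a false-positive rate. The stated sample size and power are correct and unaffected.

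**What to change.** 1. Name and lock one software version for measurement before the primary analysis, preferably before the first randomisation. Read every primary margin in both arms with it, re-reading stored scans where another version was used at the procedure.
2. Record for each patient the version used for guidance. Re-reading makes the measurement uniform; it does not undo a change in the guidance given to operators, so that change has to be visible in the data.
3. Restrict the primary comparison to concurrently randomised patients, and report experimental-only patients enrolled after a control-arm stop separately.
4. In section 1.8, part A, define the cross-validation and initial cohorts, state when the accuracy test is done, and say whether a re-optimised model may be used in patients still to be enrolled.

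The cost is a few protocol sentences, one archived software build and possibly some re-reading of stored scans. The downside is that a later, better version would not be used for the primary reading, although it could still be used for guidance. Sample size does not change.
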